16.14 Decision Rules

Analysis time point	Number of events ¹	Critical p-value		Hazard Ratio	
		Futility	Efficacy	Futility	Efficacy
50%	42	> 0.529	N/A	> 1.022	N/A
100%	83	> 0.15	≤ 0.15	> 0.797	≤ 0.797

¹ Documentation of death

16.15 Power and Sample Size

The primary goal is to compare the OS between patients who are randomized to panitumumab and those randomized to standard therapy (TAS-102 or regorafenib). The null hypothesis is that the panitumumab arm does not show a superior OS outcome compared to standard therapy (TAS-102 or regorafenib). The alternative hypothesis is that the panitumumab arm has improvement in OS compared to standard therapy (TAS-102 or regorafenib).

We will enter 53 evaluable patients to each arm of the study using a 1:1 randomization scheme (106 evaluable patients in total); unless the study is stopped early. Stratification factors are defined in section 5.0. With 53 evaluable patients per arm, we have 80% power to detect an improvement in the median OS from 6.5 to 10 months (HR=0.65), assuming a 1-sided significance level of 0.15 and an accrual rate of 8 patients per month. The trial has a single interim analysis for futility, adopting the Rho family (Rho=1.5) beta spending function for controlling the overall type II error rate and will be considered non-binding.

16.151 Operating Characteristics

The table below shows the operating characteristics assuming the OS follows the exponential survival function along with a one-sided significance level of 0.15.

The table below includes the operating characteristics according to the monitoring plan outlined above. The proportion of times that 1) the study would stop early at the interim analysis due to futility of panitumumab, and 2) the study would conclude panitumumab is superior to TAS-102 or regorafenib at the final analysis, are tabulated by true OS median survival times and equivalent true

hazard ratios for OS by treatment groups.

True median overall survival (months) ¹		True Hazard Ratio	% of times the study will be stopped for futility at the interim analysis ²	% of times that panitumumab is deemed superior at the final analysis ²
TAS-102 or regorafenib	panitumumab			
6.5	6.5	1	47.7	14.1
6.5	7.2	0.90	34.3	26.8
6.5	7.9	0.82	24.3	41.9
6.5	8.6	0.76	16.5	56.7
6.5	9.3	0.70	11.2	69.9
6.5	10	0.65	7.5	79.4

¹ Although we use the median OS to illustrate each scenario, the hypothesis testing is based on the entire survival curve.

² Proportions are based on 50,000 replicates in a simulation study

16.2 Sample Size

We plan to randomize at least 106 eligible patients (53 to panitumumab; 53 to standard therapy (TAS-102 or regorafenib). We anticipate randomizing an additional 14 patients to account for ineligibility, cancellation, major treatment violation, or other reasons. Therefore, maximum accrual is projected to be 120 patients.

16.3 Accrual Time and Study Duration

The anticipated accrual rate is approximately 8 patients per month. Therefore, the accrual period for this randomized Phase II study is expected to be around 15 months. The final analysis can begin as soon as the 83rd OS event has occurred; approximately 25 months after the study begins under the alternative hypothesis.

16.4 Data & Safety Monitoring

16.4.1 The principal investigator(s) and the study statistician will review the study at least twice a year to identify accrual, adverse event, and any endpoint problems that might be developing. The trial is monitored continually by the study team. The Mayo Clinic Cancer Center (MCCC) Data Safety Monitoring Board (DSMB) is responsible for reviewing accrual and safety data for this trial at least twice a year, based on reports provided by the study statistician. Any safety issues requiring protocol changes are communicated through protocol amendments.

16.4.2 Adverse Event Monitoring and Stopping Rules

The monitoring rule specified below is based on the knowledge available at study development. We note that the Adverse Event Monitoring Rule may be adjusted in the event of either (1) the study re-opening to accrual after any temporary suspension or (2) at any time during the conduct of the trial and in consideration of newly acquired information regarding the adverse event profile of the treatment(s) under investigation. The study team may also choose to suspend accrual because of unexpected adverse event profiles that have not crossed the specified rule below.

Accrual may be temporarily suspended to this study if at any time we observe events considered at least possibly related to study treatment (i.e., an adverse event with attribute specified as "possible", "probable", or "definite") that satisfy any of the following criteria for **each arm separately**:

- If at any time, 4 of the initial 10 treated patients, or 33% or more of all patients (when accrual is greater than 10 patients) have experienced a grade 4+ adverse event at least possibly related to treatment.

16.43 Data Safety Monitoring

This trial will be monitored by the Mayo Clinic Cancer Center Data and Safety Monitoring Board (MCCC DSMB) every 6 months.

16.5 Definitions and Analyses of Secondary Endpoints

All these endpoints will be assessed individually and will also be compared between the 2 arms. Descriptive statistics will be provided. P-values will be reported but will be considered descriptive.

16.51 Progression Free Survival (PFS)

Progression free survival is defined as the time from randomization to documentation of disease progression or death due to any cause, whichever is first. For patients who are progression-free and alive, PFS will be censored at the last disease evaluation. If the patient did not have any disease evaluation post randomization, PFS will be censored at one day after randomization. The distribution of progression free survival will be estimated using the method of Kaplan-Meier (Kaplan 1958). Progression free survival will be compared between the 2 treatment arms using the log-rank test.

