1.3 Blood-based molecular profiling to Identify Patients for EGFR Antibody Rechallenge

Several recent studies have demonstrated that molecular profiling of cell free DNA (cfDNA) could be useful for identifying patient sub-populations most likely to benefit from EGFR antibody rechallenge. As part of an investigator-initiated trial at Duke University (NCT02008383), comprehensive blood-based genomic profiling was performed on patients with EGFR-refractory, *RAS* wild-type metastatic CRC. This profiling effort utilized the Guardant360™ assay (Guardant Health, Redwood City, CA), a >70-gene NGS-based blood test. Among the 69 patients with EGFR-refractory disease who received blood-based genomic profiling, 18 patients (26%) had no detectable resistance-conferring mutation or amplification [35].

Recent studies have further shown that cfDNA profiling is an effective diagnostic tool to identify patients likely to benefit from EGFR antibody rechallenge. In a single-arm phase II study conducted in Italy (CRICKET), 28 patients with *RAS* wild-type metastatic CRC who received first-line FOLFIRI/cetuximab and second line FOLFOX/bevacizumab were assigned to third line irinotecan/cetuximab [36]. Six patients (21.5%) experienced partial response, with a median PFS of 3.4 months and a median overall survival (OS) of 9.8 months. Utilizing droplet digital (dd) PCR, 12 patients had a baseline *RAS* mutation detected in blood, and 13 patients had no baseline *RAS* mutation detected. The response rate for patients who were *RAS* wild-type in blood was 38%, with a median PFS of 4.0 months and a median survival of 12.5 months. The use of cfDNA to identify patients likely to benefit from EGFR antibody rechallenge is further supported by results of a phase II randomized trial comparing the novel EGFR antibody admixture SYM004 versus investigator choice (IC) therapy in patients with EGFR refractory metastatic CRC [37]. In the intent-to-treat (ITT) population, there was no survival benefit for SYM004 compared to IC. However, a retrospective analysis of patients who were *RAS/BRAF/EGFR* mutation negative in blood found improved survival in patients treated with SYM004 compared with IC (median OS, 12.8 and 7.3 months, respectively).

Collectively, these results support the potential clinical benefit of EGFR antibody rechallenge, and suggest that cfDNA profiling may identify patients most likely to benefit.

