3.1 Registration – Inclusion Criteria

3.11 Registered to COLOMATE ACCRU-GI-1611 and:

- a) COLOMATE Companion Trial Recommendation Form indicates patient qualifies to be screened for a COLOMATE companion trial.
- b) COLOMATE Companion Trial Recommendation Form date of completion is \leq 30 days prior to randomization.

3.12 Age \geq 18 years.

3.13 Histologically and/or cytologically confirmed adenocarcinoma of the colon or rectum that is metastatic and/or unresectable.

3.14 Documented wild-type in *KRAS* and *NRAS* (codons 12, 13, 59, 61, 117, and 146) and in *BRAF* codon 600, based on tumor tissue taken from primary or metastatic site prior to receipt of anti-EGFR therapy.

3.15 Progression, intolerance, or contraindication to a fluoropyrimidine (e.g., 5-fluorouracil or capecitabine), oxaliplatin, irinotecan, an anti-VEGF monoclonal antibody (bevacizumab, ramucirumab, or afibbercept), and an anti-PD-1 monoclonal antibody (nivolumab or pembrolizumab) if tumor has deficient mismatch repair proteins (dMMR) or is microsatellite instability-high (MSI-H).

3.16 Disease progression after treatment with an anti-EGFR monoclonal antibody (cetuximab and/or panitumumab) for at least 4 months (minimum of 8 biweekly treatments or 16 weekly treatments at full or partial dose).

NOTE: Treatments do not need to be administered consecutively.

NOTE: Dose reductions or delays are permitted.

3.17 Greater than 90 days has elapsed between the most recent treatment with an anti-EGFR therapy (cetuximab or panitumumab) and blood collection for COLOMATE ACCRU-GI-1611.

3.18 At least one site of disease that is measurable by RECIST criteria (as defined in Section 11.0) that has not been previously irradiated; if the patient has had previous radiation to the target lesion(s), there must be evidence of progression since the radiation.

3.19a Life expectancy \geq 3 months per estimation of investigator.

3.19b ECOG Performance Status (PS) 0, 1, or 2. (Form is available on the ACCRU web site).

3.19c The following laboratory values obtained \leq 7 days prior to randomization.

- Absolute neutrophil count (ANC) \geq 1500/mm³ without colony stimulating factor support
- Platelet count \geq 75,000/mm³
- Hemoglobin >8.0 g/dL
- Total bilirubin \leq 1.5 x upper limit of normal (ULN)
- Aspartate transaminase (AST) \leq 2.5 x ULN (\leq 5 x ULN for subjects with liver involvement of their cancer)

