16.0 Statistical Considerations and Methodology

16.1 Overview and Study Design

This is a randomized Phase II study which is designed to compare the overall survival (OS) in patients with EGFR refractory *RAS* wild-type metastatic CRC, who are randomized to panitumumab or standard therapy (TAS-102 or regorafenib). Prior studies have shown that the median OS is around 6.5 months for patients in this disease population receiving TAS-102 or regorafenib and PFS is around 1.9 months for patients receiving TAS-102 or regorafenib in this disease population [40, 41]. It is hypothesized that panitumumab can increase the median OS to at least 10 months. In addition to OS, this trial will also compare the overall response rate, PFS, adverse event rates, and self-reported quality of life outcomes (measured by LASA) between the panitumumab arm and standard therapy (TAS-102 or regorafenib).

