18.1 Submission Timetable

Initial Material(s) -

CRF	Active-Monitoring Phase (Compliance with Test Schedule Section 4.0)
Institutional Contacts	
On-Study	
On-Study: Prior Systemic Therapy	
Adverse Events: Baseline	
RECIST Measurements: Baseline	≤2 weeks after registration
Laboratory Tests & Results: Baseline	
Supporting Documentation: Baseline ²	
Specimen Submission: Blood (Baseline) (see	

CRF	Active-Monitoring Phase (Compliance with Test Schedule Section 4.0)
Section 14.0)	
Specimen Submission: Tissue (Baseline) (see Section 17.0)	
Patient Status: Baseline	
Notice of New Primary ¹	
OP and Path Reports (see Section 17.0) ²	
Off Treatment	Submit ≤2 weeks after registration if withdrawal/refusal occurs prior to beginning protocol therapy
Patient Questionnaire Booklet-PRO/QOL: Linear Analogue Self Assessment (LASA)	≤ 2 weeks after registration - Patient questionnaire booklet must be used; copies are not acceptable for this submission.
PRO/QOL : Booklet Compliance ³	≤ 2 weeks after registration - This form must be completed only if the (name of booklet/s – or whatever verbiage you want to use to describe the booklet/s) contains absolutely NO patient provided assessment information.
ACCRU Deviation Form ¹	Submit only if applicable during all phases of the study (initial, active and observation)

1. Submit only if applicable.
2. Upload via the Supporting Documentation: Baseline form. COLOMATE Companion Trial Recommendation Form. This is in addition to the pathology material requirements for tissue submission (Section 17.0).
3. This form must be completed **only** if the Linear Analogue Self Assessment (LASA) contains absolutely NO patient provided assessment information.

Test Schedule Material(s)

CRF	Active-Monitoring Phase (Compliance with Test Schedule Section 4.0)	
	At each evaluation during treatment	At end of treatment (within 30 days after last dose of study drug)
Treatment (Intervention)	X	X
Treatment (Intervention): Dose Modifications, Omissions and Delays ¹	X	
Adverse Events: Solicited	X	X
Adverse Events: Other ¹	X	X
RECIST Measurements ²	X	X
Supporting Documentation ²	X	X
Laboratory Tests and Results	X	X
Specimen Submission: Blood (see Section 14.0)	X	
Patient Status: Treatment (Intervention)	X	X
Notice of New Primary ¹	X	X
Consent Withdrawal (choose appropriate form) ¹	X	X
• Consent Withdrawal: Specimen Only		

CRF	Active-Monitoring Phase (Compliance with Test Schedule Section 4.0)	

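### The day-1 censoring sentence for PFS in 16.51 is not limited to living patients; applied as written, it censors deaths before the first disease evaluation that the definition counts as events

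*Combined protocol and SAP*

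**What the plan says.** Section 16.51 defines and censors PFS in three consecutive sentences.

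1. The endpoint runs from randomization to "documentation of disease progression or death due to any cause, whichever is first".
2. "For patients who are progression-free and alive, PFS will be censored at the last disease evaluation".
3. "If the patient did not have any disease evaluation post randomization, PFS will be censored at one day after randomization".

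The second sentence names the group it applies to. The third has a single condition, the absence of any evaluation after randomization, and does not mention whether the patient is alive. No other section says how PFS treats a death before the first evaluation.

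The first scheduled evaluation is at 8 weeks. Section 11.1 sets an 8-week interval, and section 4.0 places the first restaging before dosing in cycle 3, which is the same time with 28-day cycles.

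PFS is a secondary endpoint. For secondary endpoints, 16.5 says: "P-values will be reported but will be considered descriptive".

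**The concern.** A patient who dies in week 5 without a scan has an event at week 5 under the first sentence and is censored at day 1 under the third. The two readings give different analysis data sets, and the text does not say which prevails. A programmer who treats the third sentence as a specific rule overriding the general one would be following the words on the page.

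Day-1 censoring removes the patient from the risk set before any event occurs, so the death counts for nothing in the Kaplan-Meier estimate. These are the patients with the worst outcome, so the censoring is informative. Reported medians and early PFS rates would be more favourable than the protocol's own definition gives. The stake is descriptive: PFS is the first-listed secondary objective (2.21), and the background uses median PFS to compare therapies.

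**Working it through.** **Plan figures.** The plan gives no PFS calculation to reproduce. Its OS design does reproduce, which supports using its exponential model. With 83 deaths, HR 0.65 and one-sided alpha 0.15, Schoenfeld power is 82.3% before the interim look. A two-stage normal approximation with the futility look at 42 deaths gives 80.3% (16.15 states 80%, its table 79.4%). The final critical HR is 0.797, as stated.

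**Inputs**
- Control: "median OS is around 6.5 months for patients in this disease population receiving TAS-102 or regorafenib and PFS is around 1.9 months" (16.1).
- Panitumumab: median OS 10 months under the alternative (16.15).
- 53 evaluable patients per arm and exponential OS (16.15).
- First scan at 8 weeks = 56 / 30.4375 = 1.84 months.
- Assumed: exponential PFS, and a share s of early deaths that have no evaluation. The documents do not give s, so 1, 0.5 and 0.25 are shown.

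**Deaths before week 8**, as 1 − exp(−ln 2 × 1.84 / median OS)
- Control: 1 − exp(−ln 2 × 1.84 / 6.5) = 0.178; × 53 = 9.4.
- Panitumumab: 1 − exp(−ln 2 × 1.84 / 10) = 0.120; × 53 = 6.3.

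**Control patients with a PFS event by week 8**
- By the definition: p = 1 − exp(−ln 2 × 1.84 / 1.9) = 0.489.
- Under the literal rule: (p − 0.178s) / (1 − 0.178s), because the affected deaths leave both the events and the risk set.

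**Control median, ignoring the scan grid**, as 1.84 + ln[(1 − event share) / 0.5] / (ln 2 / 1.9)

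| s | Deaths censored at day 1 (of 53) | Event by week 8 | Median (months) |
|---|---|---|---|
| By definition | 0 | 48.9% | 1.9 |
| 1 | 9.4 | 37.8% | 2.44 |
| 0.5 | 4.7 | 43.9% | 2.16 |
| 0.25 | 2.4 | 46.5% | 2.02 |

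**Panitumumab at an assumed PFS HR of 0.65.** The median is 1.9 / 0.65 = 2.92. With s = 1, the event share by week 8 goes from 35.4% to 26.6% and the median from 2.92 to 3.46. The gap between arms is 2.92 − 1.90 = 1.02 months by the definition and 3.46 − 2.44 = 1.02 months under the literal rule.

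**Hazard ratio.** A simulation used 53 per arm, 4,000 trials, independent exponential progression and death, progression seen only at 8-weekly scans, follow-up of 10 to 25 months, a Cox model with Efron ties, and s = 1.

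| Scenario | HR by definition | HR under literal rule |
|---|---|---|
| True PFS HR 0.65 | 0.649 | 0.648 |
| Same progression hazard, only survival differs | 0.874 | 0.918 |
| Panitumumab median PFS 4.0 months | 0.486 | 0.458 |

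The 4.0-month scenario borrows from 1.3, where the response rate in patients *RAS* "wild-type in blood was 38%, with a median PFS of 4.0 months"; that was irinotecan plus cetuximab, so it is only an assumption here. The shifts have no constant direction. The largest on the log scale is ln(0.458 / 0.486) = −0.06, against a standard error of the log HR of about 0.20 at this sample size.

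**The case against.** The strongest reply is that the three sentences are meant to be read in order. The second opens the censoring rules for patients who are progression-free and alive. The third supplies a date when a member of that group has no last evaluation to use. On that reading the patient in the third sentence is alive and nothing conflicts. The fallback also has a natural use: someone who withdraws before the first scan needs a censoring date. This is probably the intended reading, and it stands. What it does not do is put the restriction into the text, and no other section supplies it.

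The figures are also upper bounds, and that stands too.
- A constant hazard from day 0 takes no account of 3.19a, which requires a life expectancy of at least 3 "months per estimation of investigator".
- The timetable in 18.1 lists RECIST measurements at end of treatment as well as at each evaluation, so some patients who die early may have had an evaluation. The row s = 1 is therefore a ceiling.

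A reader might infer a much larger distortion from the scan grid. With 8-weekly scans and s = 1, the typical simulated control median moves from 2.0 to 3.7 months, the week-16 scan. That jump reflects where the grid falls relative to 50%. It also lies within sampling variation: with 53 patients, the median computed by the definition has a 10th to 90th percentile range of 1.8 to 3.7. It should not be used to grade the point.

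**Conclusion.** The point holds as a minor defect of wording in a secondary endpoint. As written, the day-1 sentence reaches deaths that the definition counts as events.

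The affected patients number at most about 9 of 53 in control and 6 of 53 on panitumumab, and probably fewer. At that ceiling, the control event share by week 8 falls from about 49% to 38% (44% if half of early deaths lacked an evaluation, 47% if a quarter did). The control median moves from 1.9 to about 2.4 months, ignoring the scan grid. These figures rest on exponential OS and PFS at the plan's medians and on the assumed share s.

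Two stronger readings are not supported.
- A reader might infer that the plan will drop early deaths. The text allows this but does not establish it, and the likelier intent is the opposite.
- A reader might infer, from the unequal early-death counts, that the comparison between arms is materially biased. PFS improves in both arms, the gap in medians at a PFS HR of 0.65 is unchanged, and the HR moves little and in either direction.

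OS, alpha, power, the interim futility rule and the final decision do not use PFS and are unaffected.

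**What to change.** In 16.51, replace the day-1 sentence with:

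*A patient who dies without a post-randomization disease evaluation has an event at the date of death. Only patients alive and without progression who have no post-randomization evaluation are censored at one day after randomization.*

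This follows the protocol's own PFS definition and changes nothing if the sponsor already intended it. It needs no new data, since dates of death are already collected for OS. Sample size, event targets and visit schedule stay as they are. The cost is one sentence replaced by two, and it should be done before the PFS analysis is programmed.

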- 6 Receipt of archival tumor tissue is not required for study randomization and initiation of therapy. However, it is mandatory to receive the required tissue within 90 days from randomization. See section 17.0.
- 7 Patients have the option to complete cfDNA testing at study completion and will be allowed to re-register with protocol ACCRU-GI-1611. Site will access results by creating an account at [REDACTED] Sites will be notified by Guardant Health via email when results are available in the portal. Refer to Section 13.7. See detailed instructions on the ACCRU website under Manuals and Forms.
- 8 May discontinue day 15 visit beginning cycle 7. Additional visits and laboratory studies are permitted as per institutional practice and as clinically appropriate.
- 9 Patient must be registered prior to collection.
- 10 Patient questionnaire will be completed at baseline and each cycle (Appendix II). Patient questionnaire booklets **must** be used; copies are not acceptable for this submission. The booklet order form is located on the ACCRU website under Manuals and Forms.
- 11 If screening tests occur ≤ 7 days prior to C1D1, they do not have to be repeated prior to dosing.
- 12 The COLOMATE Companion Trial Recommendation Form must indicate that the patient has met molecular eligibility to screen. The patient must be registered to the companion study ≤30 days from date of COLOMATE Companion Trial Recommendation Form completion. If the COLOMATE Companion Trial Recommendation Form recommends a different companion study, patient may still enroll.
- 13 The diary must begin the day the patient starts taking the medication and must be completed per protocol and returned to the treating institution OR compliance must be documented in the medical record by any member of the care team.

R Research funded.

Event Monitoring: survival follow-up will be done every 3 months (± 7 days) until 3 year after randomization.

5.0 Stratification Factors:

- 5.1 Primary tumor location: right (cecum, ascending colon, hepatic flexure, and transverse colon) vs left (splenic flexure, descending colon, sigmoid colon, rectosigmoid junction, and rectum).
- 5.2 Prior TAS-102 or regorafenib: Yes vs No.

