6.2 Randomization Procedures

- 6.21 The factors defined in Section 5.0, together with the registering membership, will be used as stratification factors.
- 6.22 After the patient has been registered into the study, the values of the stratification factors will be recorded, and the patient will be assigned to

one of the following treatment groups using the Pocock and Simon [39] dynamic allocation procedure which balances the marginal distributions of the stratification factors between the treatment groups.

- Panitumumab
- Standard Therapy (regorafenib or TAS-102)

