16.12 Interim Analysis

One interim analysis for futility will be conducted when at least 42 patients across both arms combined have provided documentation of death. Overall survival will be used as the endpoint for the interim analysis. The interim futility boundary was selected using EAST software. Un-stratified log-rank p-value will be used for decision making. The trial will continue accrual while the interim analysis is being conducted. If the 1-sided p-value > 0.529 for panitumumab compared to standard therapy (TAS-102 or regorafenib), which corresponds to a hazard ratio (HR) > 1.022 , the panitumumab will be considered as futile and the accrual will be suspended. Otherwise, if the 1-sided p-value ≤ 0.529 (HR ≤ 1.022), the study will continue to full accrual and the final analysis will be conducted as described below.

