16.13 Final Analysis

Efficacy analysis will be conducted when at least 83 death events, across

both arms combined, have been observed. The stratified log-rank test will be used for decision making except when there are 0 events in any of the strata; in that case, the un-stratified log-rank will be used for decision making. If the 1-sided p-value is > 0.15 for panitumumab compared to standard therapy (TAS-102 or regorafenib), which corresponds to a hazard ratio (HR) > 0.797 , panitumumab will be considered as ineffectual; if the 1-sided p-value ≤ 0.15 (equivalently, HR ≤ 0.797), panitumumab will be considered as promising for future study. All eligible patients who sign the consent form, are randomized, and received any protocol treatment are considered evaluable for this endpoint.

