16.52 Overall Response Rate (ORR)

Overall response rate is defined as the number of patients with a complete response (CR) or partial response (PR) (as defined by the RECIST 1.1) divided by the number of evaluable patients in each arm at 12 months post registration. ORR will be compared between the 2 treatment arms. Confidence intervals for the true success proportion will be calculated according to the approach of Clopper and Pearson.

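### PFS is compared with a log-rank test that ignores the randomisation factors, although the final OS test is stratified; stratifying it to match costs almost nothing.

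*Combined protocol and SAP*

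**What the plan says.** - Section 16.51, on PFS: "Progression free survival will be compared between the 2 treatment arms using the log-rank test". The test carries no label, stratified or un-stratified.
- Section 16.13, on final OS: "The stratified log-rank test will be used for decision making except when there are 0 events in any of the strata", in which case the un-stratified test decides. The strata are not listed there.
- Section 16.12, on interim OS: "Un-stratified log-rank p-value will be used for decision making".
- Section 5.0 names two factors. The first is "Primary tumor location: right (cecum, ascending colon, hepatic flexure, and transverse colon) vs left"; the second is prior TAS-102 or regorafenib, yes or no. Section 16.15 refers to Section 5.0 for the stratification factors.
- Section 6.21, on allocation: "The factors defined in Section 5.0, together with the registering membership, will be used as stratification factors". The method is Pocock-Simon dynamic allocation.
- Section 16.5, covering all secondary endpoints: "P-values will be reported but will be considered descriptive".

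PFS is the first secondary objective (Section 2.21). Significance level and power are set for OS only (Section 16.15).

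**The concern.** When allocation is balanced on factors that predict outcome, a test that ignores them uses a variance that is too large for the design and an effect that is diluted toward the null. It stays valid but becomes conservative. The plan accepts this reasoning for the final OS test and does not carry it to PFS.

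Two practical consequences follow. First, PFS will be read beside OS. If one test is stratified and the other is not, a difference between the two results may partly reflect the method. Second, prior exposure is tied to the comparator: under Section 7.12, a control patient who has had one of the two oral drugs may receive only the other. A comparison within that stratum is therefore easier to interpret than one that pools over it.

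Sections 16.12 and 16.13 both state whether their log-rank test is stratified, and Section 16.51 does not. The plain reading is un-stratified. The alternative reading is that the choice is left open until the data are in. The remedy is the same for both.

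**Working it through.** **Step 1. Reproduce the plan's own design figures (OS).** Inputs from Sections 16.12 to 16.15: 83 deaths, HR 0.65 (6.5/10), one-sided 0.15, 1:1 allocation, futility look at 42 deaths with p > 0.529.

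- Final critical HR: exp(-2 × z(0.85)/√83) = exp(-2 × 1.036/9.110) = 0.797. The plan says 0.797.
- Interim HR: exp(-2 × z(0.471)/√42) = 1.023. The plan says 1.022.
- Power without the interim look: Φ(√83 × |ln 0.65|/2 - 1.036) = Φ(1.962 - 1.036) = 82.3%.
- Power with the futility look (bivariate normal, correlation √(42/83)): 80.3%. The plan says 80%, and 79.4% in its operating-characteristics table.

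The OS design reproduces. The documents contain no PFS power figure to reproduce.

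**Step 2. Effect of stratifying PFS.** From the documents: 106 patients randomised 1:1, two binary factors giving four strata, and a control median PFS of 1.9 months (applied to the reference stratum). Assumed, because the documents give no values: PFS HR 0.80, 0.65 or 0.50; PFS tested at one-sided 0.15 (borrowed from OS); factor prevalences of 20% to 30%; factor hazard ratios from 1 to 3; exponential times; censoring uniform between 12 and 27 months. Arms were balanced almost perfectly within strata, which is closer balance than Pocock-Simon guarantees. Each setting had 6,000 replicates, with both tests run on the same simulated data.

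Power, un-stratified → stratified (difference in points, taken before rounding):

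| Factor HRs | Prevalences | PFS HR 0.80 | PFS HR 0.65 | PFS HR 0.50 |
|---|---|---|---|---|
| 1, 1 | 20%, 20% | 53.4 → 52.2 (-1.2) | 87.2 → 85.8 (-1.4) | 99.3 → 99.2 (-0.1) |
| 1.5, 1.2 | 20%, 20% | 53.6 → 53.3 (-0.3) | 86.6 → 85.9 (-0.6) | 99.3 → 99.1 (-0.2) |
| 1.5, 1.5 | 20%, 30% | 52.9 → 52.9 (0.0) | 85.8 → 85.7 (-0.1) | 99.1 → 98.9 (-0.2) |
| 2, 1.5 | 20%, 30% | 52.0 → 53.1 (+1.1) | 84.9 → 85.5 (+0.6) | 98.8 → 98.9 (+0.1) |
| 2, 2 | 30%, 30% | 49.1 → 52.8 (+3.6) | 82.5 → 85.2 (+2.7) | 98.6 → 99.2 (+0.6) |
| 3, 2 | 30%, 30% | 46.1 → 52.5 (+6.4) | 81.1 → 86.1 (+5.0) | 98.1 → 99.0 (+0.9) |

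Monte Carlo error on each power is at most √(0.25/6000) = 0.65 points. The overall range is -1.4 to +6.4 points. At one-sided 0.025 the same grid gives -2.7 to +11.2.

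**Step 3. Reading the table.** With factor HRs between 1.2 and 2 and a PFS HR of 0.65, the change is under 1 point either way in the settings with prevalences of 20% to 30% and at most one factor HR at 2. A clear gain needs strong factors, such as both HRs at 2 or above. The small loss when neither factor is prognostic comes from splitting 106 patients into strata: at 20% prevalence each, the smallest stratum expects 106 × 0.2 × 0.2 = 4.2 patients.

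**The case against.** The strongest reply is that nothing is decided on PFS. Section 16.5 makes its p-value descriptive, no power or significance level is set for it, and an un-stratified log-rank test does not inflate false positives. This stands, and it limits the point to a free improvement. It does not explain why the two tests should differ.

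The contrast with OS is also not uniform. The interim OS test is un-stratified, the final test has an un-stratified fallback, and allocation uses registering membership as well, so a two-factor test does not mirror the allocation completely. This also stands, but it gives no reason to leave out the two clinical factors.

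A reader might infer more than the documents support:

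- **That a definite amount of PFS power is given up, or that stratifying can never lose power.** Neither follows. The size rests on assumed inputs, and the change is slightly negative when the factors are weak.
- **That the PFS and OS hazard ratios are on different scales.** No Cox model is specified anywhere in the documents. The HR of 0.797 in Section 16.13 is the value that corresponds to the p-value cutoff, so there is no stated OS estimator to compare with.
- **That response has the same fault.** Section 16.52 says only "ORR will be compared between the 2 treatment arms" and names no test, which is missing detail, not a chosen un-stratified analysis. A four-stratum Cochran-Mantel-Haenszel test would also suit it poorly: with the 1.6% response rate for TAS-102 in Table 1, 53 control patients give 53 × 0.016 = 0.85 expected responders.

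**Conclusion.** The point holds as a low-cost improvement to the PFS analysis. As written, the PFS test takes no account of two factors on which the arms are balanced, which makes it somewhat conservative if those factors are prognostic and inconsistent with the final OS test. Under the assumed prognostic strengths, prevalences and PFS effects, and with the OS level of one-sided 0.15 borrowed for PFS, stratifying moves power by about -1 to about +6 points. Moderate factors give close to no change. No planned power is lost and no trial decision changes. The argument rests mainly on consistency with OS and on settling the method in advance, and only secondarily on power.

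**What to change.** In Section 16.51, specify the log-rank test stratified by the two Section 5.0 factors (tumour side; prior TAS-102 or regorafenib), with the same fallback to the un-stratified test as in Section 16.13 when any stratum has 0 events. State that any reported PFS hazard ratio comes from a model with the same strata.

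The cost is a sentence or two in the statistical section, with no new data and no effect on the OS decision rule. The downside is a loss of about 1 point of PFS power at one-sided 0.15 if neither factor is prognostic. Leave the interim OS test in Section 16.12 unchanged, and do not extend the stratified test to ORR or clinical benefit rate.
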